5.5.2 Presentation of Hypothesis Tests

Mixed effect models will be performed between LY900014 and Humalog[®] using SAS procedure PROC MIXED. Least square means (LS-means), LS-mean differences or ratios, corresponding confidence intervals (CIs) and p-values will be presented.

Unless otherwise noted, all tests of treatment effects will be conducted at a 2-sided alpha level of 0.05, and CIs will be calculated at 95%, 2-sided.

5.5.3 Baseline Definition

If not stated otherwise baseline is defined as the last assessment prior to first drug intake unless otherwise stated.

Statistical Analysis Plan				
Trial ID	EudraCT-No.	Date	Status / Version-No.	Page
I8B-MC-ITST	2019-003493-13	15 Jul 2020	Final 1.0	30 of 47

PK parameters for Day 1 (Missed Bolus following Meal): For each day and period, the average of the two samples (pre-bolus) collected immediately prior to the correction bolus will represent as the 0-min time point for each subject, and will be used to subtracting the baseline value for all post-dose insulin lispro measurements.

PK parameters for Day 2 (Basal insulin suspension): As each subject will suspend their own individual basal rate, insulin lispro concentration at the time of administration of the correction bolus may vary from being detectable to undetectable (<LLOQ). Due to this, the PK parameters will be calculated using the CFBL insulin lispro concentrations following the correction bolus (as described in the Day 1 analysis above).

The calculation of baseline corrected AUC (iAUCs) may be explored to address possible inter-occasion variability. If conducted, the average of the two samples (pre-bolus) used to confirm the high glucose threshold (<240mg/dl) which was collected immediately prior to the correction bolus will represent as the 0-min time point for each subject, and will be used to subtracting the baseline value for all post-dose glucose measurements.

5.6 Analysis and Presentation of Demographic and Baseline Characteristics

Demographic and baseline characteristics will be presented for all subjects in the FAS.

Individual demographic and background characteristics will be presented together with standard descriptive statistics as described above and will be presented in subject data listings.

The pre-existing conditions and medical history will be summarized using frequency tables. The presentation will be done by system organ class (SOC) and preferred term, ordered in alphabetic order.

5.7 Analysis of Primary Endpoints Time to Recovery from Hyperglycaemia

The PD parameters will be determined and analyzed using software SAS Version 9.4.

Subjects who did not keep identical insulin lispro doses for LY900014 and Humalog[®] for each day and period or had differences in the consumption of the test meal will be excluded from the statistical analysis of the PD parameters. Additionally, subjects which required a rescue insulin dose during the treatment assessment period would be excluded in the analysis for both treatments (LY900014 and Humalog) periods for that day (missed bolus following meal or basal insulin suspension) since an accurate comparison of the treatment difference would not be possible. Subjects excluded from the analysis will be identified by Lilly.

Statistical Analysis Plan				
Trial ID	EudraCT-No.	Date	Status / Version-No.	Page
18B-MC-ITST	2019-003493-13	15 Jul 2020	Final 1.0	31 of 47

For the primary endpoint, comparison between the treatments will be performed per day (Day 1: meal test procedure with missed meal bolus, Day 2: basal insulin suspension) using a linear mixed model analysis of variance (ANOVA) with raw endpoint as response, treatment, period and sequence as fixed effects and subject within sequence as a random factor.

Within the model, least squares means of LY900014 and Humalog[®], differences in LS-means and the corresponding 95% CI for the treatment difference will be estimated. The p-value on the difference between LS-means will be used to determine statistical significance. The treatment ratio and 95% CI for the ratio will be calculated using Fieller's theorem [4].

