5.3 Blinding and Code Breaking Procedures

This is a subject- and investigator-blind randomized trial. The CRU personnel who will prepare the pump reservoirs for each treatment period and the syringe for correction bolus administration on Day 2 and administer the drug (only on Day 2, Day 1 administration can be done by blinded personnel) will not be blinded and will be separate and distinct from those who are involved in subject care. The sponsor including the Lilly CP/Lilly study team will be unblinded. Blinding will be maintained throughout the conduct of the study as described in a separate blinding document.

Treatment assignment will be kept strictly confidential and accessible only to authorized persons until after the time of un-blinding. Codes with treatment assignment will, however, be readily available to the blinded personnel in case of an emergency.

Clinical Trial Protocol				
Trial ID	EudraCT-No.	Date	Status / Version-No.	Page
I8B-MC-ITST	2019-003493-13	17 Jan 2020	Final 2.0	28 of 74

Two sets of sealed codes with the subject randomization number containing information about the treatment at each visit will be prepared for each subject. One set will be kept at the trial site in the office of the physician on duty (during the entire trial period), the other set will be kept under the responsibility of the Sponsor and are to be used in case of code break need.

The code for a particular subject may be broken by an investigator in case of a medical emergency if knowing the identity of the treatment allocation could influence the treatment of the subject. Whenever a code is broken, the person breaking the code must record the time, date and reason as well as his/her initials in the source documents and on the code envelope. The breaking of blinded codes in case of medical emergency for one subject should not unblind the trial personnel to the treatment information of other subjects. The person performing the unblinding should inform as few people as possible about the result of the unblinding. All persons unblinded for a specific subject should be documented.

If the trial site needs to break the code, the Sponsor should, if possible, be contacted prior to breaking the code. In all cases, the monitor must be notified within 24 hours after the code has been broken.

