13.2 Selection of Subjects for Analyses

The following analysis sets are defined in accordance with the ICH-E9 (6) guidance:

Full Analysis Set (FAS)

The full analysis set (FAS) is based on the intention-to-treat principle and includes all subjects who were treated with IMP. Subjects will contribute to the evaluation 'as randomized'.

Modified FAS (mFAS)

The modified FAS includes all subjects of the FAS who complete the study according to the sequence/treatment to which they are randomized. Subjects will contribute to the evaluation 'as randomized'. Primary and secondary statistical analyses of PK and GD parameters will be conducted on the set of subjects who complete all treatment periods with the same dose and meal intake **CCI**

Safety Analysis Set

The safety analysis set includes all enrolled subjects, whether or not they fulfilled all protocol requirements. Subjects in the safety set will contribute to the evaluation 'as treated'. The safety analysis will be based on the safety analysis set.

Clinical Trial Protocol				
Trial ID	EudraCT-No.	Date	Status / Version-No.	Page
I8B-MC-ITST	2019-003493-13	17 Jan 2020	Final 2.0	62 of 74

Before data are released for statistical analysis, a blinded review of all data will take place to identify protocol deviations that may potentially affect the results. This review will be performed without revealing which IMP the subjects are assigned to. The blinding of the IMPs will be maintained for everyone involved in allocating subjects to the analysis sets until data are released for statistical analysis. Obviously erroneous data points may be excluded from the analyses or re-analysed (in case of e.g. serum concentrations). The decision to re-analyse or exclude data points from the statistical analysis is the joint responsibility of the Sponsor, the Principal Investigator and the Trial Statistician.

The subjects or observations to be excluded and the reason for their exclusion will be documented and signed by those responsible prior to database lock. The documentation will be stored together with the remaining trial documentation. The subjects and observations excluded from analysis sets, and the reason for this, will be described in the clinical study report.

Subjects withdrawn from the trial will be listed including the primary reason for withdrawal.

If deemed necessary further endpoints and/or analyses may be added to the SAP. Only analyses not specified in the SAP will be considered as post-hoc analyses.

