4.3 Assessments for Pharmacodynamics

Eli Lilly will be responsible for the derivation of the PD endpoints and will provide the derived PD endpoints to Profil Institut für Stoffwechselforschung GmbH, Neuss, Germany.

For each study day (Day 1: meal test procedure with missed meal bolus and Day 2: basal insulin suspension), the primary endpoint time to recovery from hyperglycemia after administration of a correction bolus will be determined per subject and period. The determination of the time to recovery after administration of a correction bolus will be calculated from the time of correction bolus administration until the time of the exact point of time when PG is 140 mg/dL, which will be determined using linear interpolation.

Similarly, for each study day, the key secondary PD endpoints include: glucose AUCs, PG_{max} and rate of change in PG will be determined.

The secondary endpoint rate of change in PG will be defined as the change in PG at the time of bolus IMP administration (B) to PG at 140 mg/dl divided by the duration of time for this interval, based on individual measurements per subject, period and day.

The following secondary GD AUCs will be calculated per patient, period and day:

- the area under the PG curve, but above 140 mg/dL from time of correction bolus to the time that the PG is 140mg/dl ($AUC_{B-1PG140}$) and

Statistical Analysis Plan				
Trial ID	EudraCT-No.	Date	Status / Version-No.	Page
I8B-MC-ITST	2019-003493-13	15 Jul 2020	Final 1.0	20 of 47

- the area under the PG curve but above 180mg/dL from time of the correction bolus to the time that the PG is 180mg/dl ($AUC_{B-tPG180}$).

The AUCs will be calculated using the linear trapezoidal rule and using the actual times along with the time when PG is 140 mg/dL or 180mg/dL, which will be determined using linear interpolation. Additionally, calculation of baseline corrected AUC (iAUCs) using the PG at the administration time of the correction bolus may be explored to address possible inter-occasion variability.

The secondary GD endpoint PG_{max} will be determined individually per subject, period and day based on measured PG values.

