5.2 Protocol Deviations

During database cleaning, the unblinded SDTM data will be provided to Sponsor and to two Profil statisticians. This will still maintain the blinding as those individuals with access to the dataset will not be involved in the data base release (DBR) meeting. The statistical analysis will be provided on unblinded data before DBR.

Deviations from the protocol will be assessed as “important” or “non-important” in agreement with the sponsor. Protocol or procedure deviations are defined as “important” if they are likely to affect the outcome of the trial (e.g. effect on target variables). All other protocol and procedure

Statistical Analysis Plan				
Trial ID	EudraCT-No.	Date	Status / Version-No.	Page
I8B-MC-ITST	2019-003493-13	15 Jul 2020	Final 1.0	28 of 47

deviations are regarded as non-important. For important protocol and procedure deviations a description will be given in the CSR.

The subjects or observations to be excluded and the reason for their exclusion will be documented. Lilly's SOP for data exclusion will be followed. A sensitivity analysis may be conducted to assess the impact of data exclusion on the analysis. The reason for exclusion of subjects and details of the sensitivity analysis will be described in the CSR.

Subjects withdrawn from the trial will be listed including the primary reason for withdrawal.

In any case all decisions to correct or exclude values must have a reasonable foundation and must be documented in the meeting minutes.

New NTFs, protocol and procedure deviations may be written after the meeting as a result of findings and decisions during the DBR meeting.

The blinded review is completed after signing the DBR meeting minutes prior to database lock.

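### The unblinded sponsor identifies who leaves the primary analysis, the blinded sign-off follows the treatment-coded analysis, and what counts as Day 2 rescue insulin is left open

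*SAP*

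**What the plan says.** **Who selects.** On the primary endpoint, SAP 5.7 ends its exclusion paragraph with "Subjects excluded from the analysis will be identified by Lilly". Protocol 13.2 says: "The blinding of the IMPs will be maintained for everyone involved in allocating subjects to the analysis sets until data are released for statistical analysis". Protocol 5.3 says: "The sponsor including the Lilly CP/Lilly study team will be unblinded"; SAP 5.18 repeats this for the study team. SAP 4.3 adds: "Eli Lilly will be responsible for the derivation of the PD endpoints".

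**Order of steps.** Protocol 13.2 puts a blinded review of all data before release for analysis. Under SAP 5.2, during cleaning, "the unblinded SDTM data will be provided to Sponsor and to two Profil statisticians". The analysis is run on unblinded data before database release (DBR), and the blinded review is complete only once the DBR minutes are signed.

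**Safeguards.** SAP 5.2 states that "those individuals with access to the dataset will not be involved in the data base release (DBR) meeting", has exclusion decisions minuted and refers to a sponsor SOP on data exclusion. Protocol 5.3 adds: "Blinding will be maintained throughout the conduct of the study as described in a separate blinding document". SAP 5.1, 5.5.1, 5.14 and 5.15 provide listings that show excluded subjects, excluded observations and administered doses.

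**What is excluded.** Protocol 13.4.1 removes subjects with unequal insulin lispro doses or test-meal differences. SAP 5.7 keeps these rules and adds that a subject needing a rescue insulin dose loses both periods for that day, because a fair comparison would no longer be possible.

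**Day 2 additional insulin.** Protocol Table 3 has an additional correction bolus at B+2h if PG is above 180 mg/dL. Protocol 8.8.1 has an additional bolus, for both procedures, if PG stays above 306 mg/dL for more than 1 hour or if the investigator judges it necessary.

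**The concern.** A list of exclusions from a primary analysis is credible when the people who settle it cannot see treatment or results. Here the party named in SAP 5.7 can see both, and nothing in that section limits the task to blinded sponsor staff. The formal blinded sign-off then comes after a treatment-coded result already exists.

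This matters most where a criterion needs interpretation. Dose and meal differences can be read from recorded data. The Day 2 rescue criterion cannot be fully applied that way: the SAP does not say whether the Table 3 bolus is rescue, or whether any additional bolus is dose under the identical-dose rule. The Table 3 bolus is given because glucose is still high two hours after correction, so excluding its recipients removes slow recoveries. Slow recovery is the endpoint. The choice can therefore change both the number analysed and the estimate, and the only check on it, a sensitivity analysis in SAP 5.2, is optional.

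**Working it through.** **1. The texts side by side**

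| Question | Protocol 13.2 | SAP |
|---|---|---|
| Who settles the analysis set? | People blinded to treatment | Sponsor identifies exclusions (5.7); sponsor is unblinded (5.18) |
| Review or analysis first? | Blinded review, then release | Unblinded analysis, then signed DBR minutes (5.2) |
| Does the DBR safeguard cover the 5.7 step? | Not applicable | Not stated |

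The conflict is not only between SAP and protocol. Protocol 13.2 also says that the decision to re-analyse or exclude data points "is the joint responsibility of the Sponsor, the Principal Investigator and the Trial Statistician", and protocol 13.5 lets the sponsor team analyse data while the trial is ongoing.

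**2. The Day 2 wording.** There are two possible answers to each of two questions. Is the Table 3 bolus rescue? Is it dose? This gives three analysis sets:
- A1, neither rescue nor dose: all recipients stay.
- A2, dose but not rescue: recipients in one period only are dropped; those treated in both periods stay (if their total doses match).
- B, rescue: every recipient is dropped.

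SAP Appendix 2 does not settle it, as it covers only Days -1 and 1. SAP 5.9 repeats the rescue exclusion and SAP 5.8 omits it.

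**3. The plan's own sample size.** Inputs (protocol 13.1): difference 32 min, power 80%, SD 78 min, a crossover figure of about 55, 24 completers; two-sided 0.05 (protocol 13.2).

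N = ((1.960 + 0.842) × SD of differences / 32)². With 55 as the SD of within-subject differences, N = 23.2, so 24: reproduced. The noncentral t (N − 2 df) gives 77.8% power at 24. If 55 is instead the root mean square error, the SD of differences is 55 × √2 = 77.8. The documents do not say which, so both 55 and 78 are carried below.

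**4. Loss of numbers alone.** Two-sided power for 32 min (noncentral t):

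| Analysed | SD of differences 55 | SD of differences 78 |
|---|---|---|
| 24 | 77.8% | 48.5% |
| 22 | 73.8% | 44.9% |
| 20 | 69.2% | 41.2% |
| 18 | 64.0% | 37.3% |
| 16 | 58.2% | 33.4% |

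**5. Choosing between readings.** Assumption, not in the documents: on average 2, 4, 6 or 8 of 24 subjects receive the Table 3 bolus in at least one period. The simulation used 160,000 crossovers per setting, 12 subjects per sequence, a period-adjusted t-test, total SD 78 and within-subject correlation 0.5 (SD of differences 78 × √(2 × 0.5) = 78) or 0.75 (78 × √(2 × 0.25) = 55). The bolus is represented by a long recovery time; its effect on recovery is not modelled.

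| Quantity, over 2 to 8 recipients and both SDs | A1 or B (not dose) | A2 or B (dose) |
|---|---|---|
| One-sided false-positive rate if the better reading is chosen (nominal 2.5%) | 3.2-4.1% | 2.5-3.4% |
| Readings disagree on significance, true difference 32 min | 11-33% | 1-14% |
| Disagreement from random removal of the same number | 8-26% | 1.5-16% |

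At a true 32 min, the mean estimate under B is 29.0-30.2 min with 2 recipients and 24.1-26.9 min with 8. Under A2 it is 28.8-29.9 and 23.0-25.7 min, so A2 and B differ by about 0.2-1.2 min. Only 0.2-3.2 subjects on average have the bolus in both periods and stay ambiguous under A2.

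**The case against.** The best case for the plan has four parts.

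- *The protocol allows it.* It unblinds the sponsor, lets it analyse during the trial and gives it a joint role in excluding data points. This stands: the SAP did not create the whole problem. But the joint role concerns data points, and the same section still demands blinding for set allocation.
- *Identifying may only mean flagging.* Holders of unblinded data stay out of the DBR meeting, decisions are minuted, and the listings let anyone check an exclusion against recorded doses. The SOP and the blinding document, neither available here, may add more. This limits the concern. It does not close it, because SAP 5.2 does not route the 5.7 list through that meeting, and a listing shows who was excluded, not when the decision was made.
- *The rescue rule is stated with its reason, and its meaning can be inferred.* SAP 3.1 uses rescue for the 306 mg/dL rule on Day 1, which protocol 8.8.1 applies to both procedures. Table 3 uses a different term, and protocol 5.4 says correction doses should in general match between periods, which favours counting the bolus as dose and hence the smaller figures. Yet the reason given in SAP 5.7 leans towards excluding after any extra insulin. The inferences pull in different directions.
- *The exclusion mostly works against finding a difference.* In the not-dose case, moving from A1 to B loses significance in about 9-30% of simulated trials and gains it in about 2-4%. This is correct and argues against assuming a favourable bias. The estimate still depends on the reading.

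A reader might infer that exclusions were chosen after the results were seen, perhaps because the SAP is dated 15 July 2020 and the last visit was planned for June 2020. The documents do not support that: protocol 5.5 says timelines may vary, no actual dates are given, and the investigator who orders extra insulin is blinded.

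**Conclusion.** The point holds as a gap in process and wording. SAP 5.7 and 5.2 do not meet the blinding and ordering that protocol 13.2 sets, and the protocol's own permissions contribute to this. The safeguards are real but are not tied to the identification step, and sign-off follows the treatment-coded analysis. From the two documents alone, one cannot confirm that the Day 2 set is fixed independently of the result.

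The size is uncertain. The figures rest on an assumed 2 to 8 recipients, a proxy for the bolus and no modelled bolus effect. In the not-dose case, much of the disagreement is simply lost sample size; in the dose case, it is no more than random removal gives. It would be wrong to read the 3.2-4.1% as the error rate of this trial or as an effect of unblinding, which has not been measured. It would also be wrong to say that Day 2 has no rescue rule: SAP 5.7 names basal insulin suspension, and only the trigger and the dose question are open. It should be fixed because this is the primary analysis and the remedy is cheap. Confidence is moderate.

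**What to change.** 1. Amend SAP 5.2 and 5.7. The sponsor may flag candidates, but blinded DBR participants apply the written rules to treatment-masked dose, meal and additional-bolus data. They sign the exclusion list before any treatment-coded analysis is used for the primary result. Align protocol 13.2, protocol 13.5 and SAP 5.18 with this.
2. Before that sign-off, state for analysis purposes only whether each type of additional bolus (Table 3 at B+2h; section 8.8.1) counts as a rescue insulin dose, and whether it counts as dose under the identical-dose rule. Apply the answer consistently in SAP 5.7, 5.8 and 5.9. Table 3 and section 8.8.1 must be reconciled with the exclusion rule; no clinical rule is proposed here.
3. Make one sensitivity analysis mandatory: the primary model with the available data of rescue-excluded subjects included.

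Listing the rescue exclusion in SAP section 9 would be an editorial improvement.

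The cost is SAP wording and the matching protocol alignment, a change in the order of two existing steps, one extra model run and slightly later treatment-coded output.

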5.8 Analysis of Secondary PD Endpoints

Subjects who did not keep identical insulin lispro doses for LY900014 and Humalog[®] for each day and period or had differences in the test meal will be excluded from the statistical analysis of the PD parameters.

Log-transformed PG AUCs and PG_{max} will be evaluated to estimate geometric LSmeans, ratios of geometric means of insulin lispro within LY900014 to Humalog[®], and their corresponding 95% CIs of the ratios using the mixed-effects model that includes treatment (LY900014, Humalog[®]), period and sequence as fixed effects and subject within sequence as a random effect.

Within the model the LS mean for each treatment as well as the difference of the LSmeans between the treatment groups and corresponding 95% CI will be calculated and exponentially back-transformed in order to find the estimated ratio between the insulin formulations and corresponding 95% CI.

The analysis will be performed separated by day (Day 1: meal test procedure with missed meal bolus, Day 2: pump suspension). In case of determination of baseline corrected AUCs (iAUC) to address possible inter-occasion variability, iAUCs will be analysed using the same model. Analysis of iAUCs will be based on untransformed endpoints, if negative values occurred. In this case, LS-means, treatment differences in LS-means, and corresponding 95% CIs for the treatment differences will be estimated from the model. The p-value on the difference between LS-means will be used to determine statistical significance. The treatment ratios and 95% CIs for the ratios will be calculated using Fieller's theorem.

The same model without log transformation will be used for the analysis of the rate of change in PG and exploratory PD time parameters. LS-means, treatment differences in LS-means, and the corresponding 95% CIs for the treatment differences will be estimated from the model. The p-

Statistical Analysis Plan				
Trial ID	EudraCT-No.	Date	Status / Version-No.	Page
I8B-MC-ITST	2019-003493-13	15 Jul 2020	Final 1.0	32 of 47

value on the difference between LS-means will be used to determine statistical significance. The treatment ratios and 95% CIs for the ratios will be calculated using Fieller's theorem [4].

